5. CHANGES TO PLANNED ANALYSIS FROM PROTOCOL

Screening and enrollment for the placebo-controlled cohort 2 of the study were terminated by sponsor following the communication letter titled 'Enrollment Communication' dated 18Mar2024. Consequently, the study now comprises only one treatment group (IMG 300 mg). Henceforth, all analyses and result reporting will involve only one treatment group. Analyses related to the placebo-controlled cohort (i.e., cohort 2) are no longer applicable and this will not be reported.

6. STATISTICAL METHODS

For continuous variables, at the reported visits or in overall summary, descriptive statistics will consist of number of participants with observations (n), mean, median, standard deviation (SD),

minimum, and maximum. It is noted that number of participants with observations could include participants with data that were observed as well as those that were imputed for specific types of missing data or determined based on handling of intercurrent events, as explained in later sections.

For categorical variables, frequencies and percentages will be displayed for each category.

In the context of efficacy-related tables, percentages will be calculated based on the denominator of number of participants with data depending on the handling of intercurrent events as well as imputations of missing data as explained in the later sections. For non-efficacy tables, percentages will be calculated based on the corresponding analysis population unless otherwise specified in the mock shell.

Listed below are some subgroups for potential exploratory subgroup analysis:

- Race (Black/African American vs. Non-Black/Non-African American)
- Age group (18-64 years old vs. ≥ 65 years old)
- EASI Score at baseline (EASI ≤ 21 (moderate) and EASI > 21 (severe))
- Disease severity based on IGA score (moderate, defined as IGA at baseline =3 vs. severe, defined as IGA at baseline =4)
- Baseline TARC [REDACTED]
- Age at disease onset (≤ 12 years old vs. > 12 years old)
- Presence of atopic comorbidities (Yes vs. No)
- History of biologics/JAK-I failure

6.1 Demographics and Baseline Characteristics

Demographics and Baseline Characteristics will be summarized based on safety analysis set. Listing of demographics and baseline characteristics will be presented.

6.2 Medical and AD History

Non-atopic medical history and comorbid (concomitant) non-atopic medical illness will be summarized by primary system organ class (SOC) and preferred term (PT). Atopic disease history and comorbid (concomitant) atopic medical illness will be summarized separately in the safety analysis set by type of disease. The table will be sorted by decreasing frequency of SOC followed by PT (or disease type in case of atopic disease history).

Medical history will be listed by SOC and PT, based on the safety analysis set.

6.3 Prior and Concomitant Medications/Procedures for AD

Below summaries will be provided on prior and concomitant medications/procedures for treatment of AD for the safety analysis set, sorted by decreasing frequency of anatomic therapeutic class (ATC) level 2 (pharmacological or therapeutic subgroup) and preferred term.

- Summary of prior medications related to AD by ATC level 2 and preferred term.
- Summary of prior medications related to AD by type of medication

- Summary of prior medications related to AD by reason for discontinuation, ATC level 2 and preferred term
- Summary of prior medications related to AD by reason for discontinuation and type of medication.
- Summary of concomitant medications related to AD by ATC level 2 and preferred term.
- Summary of rescue medication (RM) by ATC level 2 and preferred term
- Summary of the duration of RM by ATC level 2 and preferred term

The duration of RM will be calculated as:

$$(\text{Date of last usage of RM} - \text{Date of first usage of RM}) + 1$$

If a participant has utilized RM on multiple occasions, the total duration will be calculated as the cumulative sum of each RM duration. A summary of the duration of rescue medications by type of medication will be presented.

Listings will be provided for prior and concomitant medications/procedures for AD and rescue medication for the safety analysis set. The listings will include ATC level 2 and preferred terms, indication, dose, frequency, route, start date, study day onset (for medications started before treatment, the study day onset (defined as date of medication start - date of the first dose; for medications started on or after treatment, the study day onset = date of medication start - date of the first dose+1), the study end date (defined similarly as for study onset day)).

6.4 Prior and Concomitant Medications for non-AD

Below summaries will be provided on prior and concomitant medications/procedures for non-AD conditions for the safety analysis set, sorted by decreasing frequency of ATC level 2 and preferred term.

- Summary of prior non-AD medications by ATC level 2 and preferred term.
- Summary of concomitant non-AD medications by (ATC level 2 and preferred term).

Listings will be provided for non-AD medications (prior and concomitant) for the safety analysis set. The listings will include reported term, ATC level 2, Indication, dose, frequency, route, start date, study day onset (for medications started before treatment, the study day onset (defined as date of medication start - date of the first dose; for medications started on or after treatment, the study day onset = date of medication start - date of the first dose+1), end date and end study day (defined similarly as for study onset day)).

6.5 Prior and Concomitant non-Drug Therapies and Procedures

Below summaries will be provided on prior and concomitant non-drug therapies/ procedures for treating AD and conditions other than AD, for the safety analysis set.

- Summary of prior non-drug therapies/procedures related to AD by SOC and PT.
- Summary of prior non-drug therapies by SOC and PT for treating conditions other than AD.

- Summary of concomitant non-drug therapies by SOC and PT for treating conditions other than AD.

A listing will be provided for non-drug therapies and procedures. The listing will include reported term, dictionary terms, Indication, start date, study day onset (defined similarly as for medications in above section), end date and end study day (defined similarly as for medications in above section).

6.6 Participant Disposition

Summaries will be provided for the following data for the full study sample (i.e., all screened participants who signed informed consent):

- The number and percentage of participants screened, and who failed screening, along with the reasons for screen failure. (This will be reported only in the overall group.)
- The number and percentage of participants included in the treatment group as well as in each study analysis set.
- The number and percentage of participants who completed the 4 week dosing period, discontinued the 4 week dosing period with the reason for discontinuation, completed the 12 week treatment period, discontinued 12 week treatment period with reason for discontinuation, completed the study, and discontinued the study with reason for discontinuation.

A summary will be provided for major protocol deviations by deviation category.

The following listings will be provided.

- The participant disposition listing comprises various details, including the date of ICF signing, ICF and protocol versions, enrolment or screen failure dates, and the completion/discontinuation date of the 4-week dosing period, date of 12-week treatment period/discontinuation, reason for discontinuation, study completion status, date of study completion, among other factors.
- A listing of screen failures with inclusion criteria not met and/or exclusion criteria met.
- Listing of protocol deviation.

6.7 Treatment Exposure and Compliance

A descriptive summary of treatment exposure will be provided on safety analysis set for the following data.

- summary of dose administered (in mg) by visit
- summary for dose-weight proportion with the categories; [REDACTED]
[REDACTED].
- The number (%) of participants who receive treatment by treatment duration (≥ 15 days and ≥ 29 days)
- Number and percentage the participants with infusion frequency (1, 2 and 3 infusions).
- Summary on overall duration of the treatment.

Overall duration of the treatment will be provided irrespective of intermittent dose interruptions. The duration of treatment exposure in the study is calculated in days as:

[REDACTED]

Categorical summary of visit wise treatment compliance showing the number (n) and percentage of participants falling within the following ranges: <80%, 80%-<100%, 100%-120%, >120% will be presented for the treatment group. The compliance with protocol-defined investigational product will be calculated as follows: Treatment Compliance= ((Actual total dose administered) / (total planned dose)) x 100%.

A listing of treatment exposure will be provided on safety analysis set, which includes start and date/time of infusion, infusion administered arm, dose, infusion rate, dose interruption, and details of dose interruption.

6.8 Analysis of Efficacy Variables

All the efficacy evaluations will be performed on modified full analysis set unless otherwise specified.

6.8.1 Analysis of Secondary Efficacy Variable

A descriptive summary (n, mean, median, standard deviation, minimum, maximum, Q1, Q3, standard error) will be provided for percentage change from baseline in EASI score at Week 12.

A mixed model repeated measure (MMRM) analysis will be performed for percentage change from baseline in EASI over time up to Week 12 by considering visit as a fixed effect, along with baseline EASI score as a covariate; unstructured covariance matrix will be used for the model errors (Alternative covariance matrices such as Compound symmetry will be used if the unstructured covariance matrix fails to converge) and Kenward-Roger (KR) approximation is used to estimate denominator degrees of freedom.

MMRM will compare the effect of IMG-007 at each post baseline visit versus the baseline based on difference relative to zero. Least square means and their corresponding 95% confidence intervals will be provided along with the p-value at nominal two-sided 5% significance level.

Based on the estimand framework introduced in [ICH E9 \(R1\)](#), additional details relating to the definition of the estimand is proposed.

Handling of intercurrent events of treatment discontinuation and rescue medication:

[REDACTED]

Handling of missing data

No missing data will be imputed for the main efficacy analysis.

Sensitivity analyses

The following two sensitivity analyses will be performed:

Line graphs will be generated to illustrate the change from baseline and percentage change from baseline (up to week 12) in the total EASI scores.

Note: Refer the [Appendix 12.7](#) for the details on the management of intercurrent events and details on primary and sensitivity analysis illustrated with some examples.

6.8.2 Analysis of Key Exploratory Efficacy Variables

6.8.2.1 Continuous efficacy endpoints

All continuous exploratory efficacy endpoints will be analyzed using the same approach as that used for the main analysis of percentage change from baseline in EASI at Week 12.

For the timepoints beyond Week 12, separate MMRM models will be developed to include all the post-baseline visits until Week 24/EOS. However, the estimates and p-values will be reported only for the timepoints beyond Week 12 from these models. The results of earlier timepoints will be reported from the models up to Week 12.

Sensitivity analyses

Line graphs will be plotted to illustrate the change from baseline and percentage change from baseline (up to week 24) in the total EASI scores. Similar line graphs will be presented for SCORAD and O-SCORAD. The X-axis will represent visit, while the Y-axis will denote the change from baseline or percentage change from baseline.

6.8.2.2 Responder type (binary) efficacy endpoints

The responder type (binary) endpoints will be reported using frequency and percentage along with the 95% Clopper-Pearson exact confidence interval for the proportion. A nominal two-sided 5% significance level will be used.

Based on the estimand framework introduced in [ICH E9 \(R1\)](#), additional details relating to the definition of the estimand is proposed.

Handling of intercurrent events (for responder type binary endpoints) of treatment discontinuation and rescue medication:

Handling of missing data

After the handling of intercurrent events explained above, missing data will be managed in two steps as given below.

- 1) Non-responder imputation will be performed for all scheduled visits following participant discontinuation from the study with the reason 'lack of efficacy'.
- 2) LOCF approach will be applied for all missing visits, except for missing data that arises following study discontinuation with reason 'lack of efficacy'.

Sensitivity analyses

No prespecified sensitivity analyses will be performed. Post-hoc sensitivity analysis will be considered as appropriate later.

Bar plots will be included to depict responder-type of endpoints of EASI and IGA. The X-axis will feature visits, and the Y-axis will represent the proportion of participants, expressed as a percentage.

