6.10 Early Withdrawal from Study

6.10.1 Discontinuation of Study Treatment

6.10.1.1 Permanent Discontinuation of Study Treatment

- [REDACTED]
- [REDACTED]
- [REDACTED]
- [REDACTED]
- [REDACTED]
- [REDACTED]

The medical monitor should be contacted as soon as feasible if study treatment is permanently discontinued in any participant due to the above reasons.

Other reasons for permanent discontinuation of study treatment include:

- Diagnosis of malignancy during the study, except for carcinoma in situ of the cervix, or squamous or basal cell carcinoma of the skin
- Occurrence of any medical condition or circumstance that exposes the participant to substantial risk and/or does not allow the participant to adhere to the requirements of the protocol

- Pregnancy
- Unblinding of study treatment for any reason in Cohort 2
- Participant failure to comply with protocol requirements or study-related procedure
- Participant receives systemic corticosteroids or non-steroidal immunosuppressive or immunomodulating medications (e.g., cyclosporin, methotrexate, azathioprine, mycophenolate-mofetil, JAK inhibitors, biologic agents, etc.)
- Participant receives a live (including live attenuated) vaccine
- Participant receives an investigational drug (other than IMG-007)
- Lack of efficacy/activity of the study treatment, defined as inadequate improvement in disease activity based on investigator's clinical judgment
- Physician decision
- Study is stopped by the Sponsor or health authority.

Note that discontinuation of study treatment does not represent withdrawal from the study. Participants who permanently discontinue study treatment before the Week 4 visit should continue with all the remaining study visits.

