6.10.2 Participant Withdrawal from the Study

In accordance with the Declaration of Helsinki and other applicable regulations, a participant has the right to withdraw from the study at any time at his/her own request or may be withdrawn at the discretion of the investigator for safety, compliance or administrative reasons.

A participant might withdraw from the study for any of the reasons below:

- Voluntary withdrawal of consent or study participation, at any time
- A participant's failure to comply with the protocol requirements or study-related procedures

- An intercurrent or safety event which, in the opinion of the investigator, requires the withdrawal of the participant
- Lost to follow-up
- Death

Participants who withdraw from the study any time before the Week 12 visit should complete the Week 12 (Day 85)/EOT visit at withdrawal. Participants who withdraw from the study early after Week 12 should complete the Week 24 (Day 169)/EOS visit at withdrawal. All information, including the reason for early withdrawal will be recorded in the participant's study records and in the CRF.

For participants who are lost to follow-up or withdraw their consent to participate in the study, the procedures of withdrawal from the study will no longer apply.

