7.1.5 End of Study

The EOS visit will be on Day 169.

The investigator may discontinue a participant's study participation at any time during the study when the participant meets the study treatment discontinuation criteria described in [Section 6.10.1](#). A participant may discontinue his or her participation without giving a reason at any time during the study. Should a participant's participation be discontinued, the primary criterion for termination must be recorded by the investigator.

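### Non-responder imputation looks for lack of efficacy at study level only, so efficacy failures recorded at an earlier disposition level can fall to LOCF

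*SAP*

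**What the plan says.** SAP section 6.8.2.2 handles missing responder data in two steps, after intercurrent events have been dealt with.

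- Step 1: "Non-responder imputation will be performed for all scheduled visits following participant discontinuation from the study with the reason" lack of efficacy.
- Step 2: "LOCF approach will be applied for all missing visits, except for missing data that arises following study discontinuation with reason" lack of efficacy.

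The protocol treats leaving the study and stopping treatment separately.

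- Section 6.10.2 opens with "A participant might withdraw from the study for any of the reasons below" and gives five: voluntary withdrawal, non-compliance, an intercurrent or safety event, loss to follow-up, and death. Lack of efficacy is not among them.
- Section 6.10.1.1 lists, as a ground for permanently stopping treatment, "Lack of efficacy/activity of the study treatment, defined as inadequate improvement in disease activity". It adds: "Note that discontinuation of study treatment does not represent withdrawal from the study".
- Section 7.1.5 connects the two: "The investigator may discontinue a participant's study participation at any time during the study when the participant meets the study treatment discontinuation criteria" of section 6.10.1. It also requires that "the primary criterion for termination must be recorded by the investigator".

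SAP section 6.6 tabulates discontinuation with its reason at three levels: the 4-week dosing period, the 12-week treatment period, and the study.

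**The concern.** The imputation rule sends one kind of dropout to non-response and everyone else to LOCF. Which way a participant goes depends on a single field, the study-level reason. The protocol places lack of efficacy mainly at treatment level, and the SAP collects reasons at two levels that the rule does not read. The trial database can therefore hold a recorded efficacy failure for a participant whose later missing visits are still filled by carrying the last status forward. If that status was a response, the responder rate is too favourable. The endpoints concerned are EASI-50/75/90 and the IGA and itch responder rates, all key exploratory. The cohort is small and uncontrolled, and protocol section 4.1 says its data are meant to inform the design of a Phase 2b study, so an upward error of one or two participants would be noticed.

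**Working it through.** The plan gives no response rate or dropout count for these endpoints, so there is no stated figure to reproduce. The check is to follow the possible routes through the visible text and then size one misrouted participant.

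**Routes**

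| What is recorded | Handling of later missing visits, visible text |
|---|---|
| Lack of efficacy as the study-level reason (possible through protocol 7.1.5) | Step 1: non-response |
| Lack of efficacy at dosing- or treatment-period level; participant stays in the study | No visits missing because of study exit |
| Lack of efficacy at dosing- or treatment-period level; participant later leaves under another reason | Step 2: LOCF |
| Lack of efficacy recorded at no level; participant leaves under another reason | Step 2: LOCF |

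The third row is the gap: the information needed for non-response is in the database, but the rule does not use it.

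**When the third row carries a response forward**

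1. Protocol section 6.10.2 says: "Participants who withdraw from the study any time before the Week 12 visit should complete the Week 12 (Day 85)/EOT visit at withdrawal". A matching Week 24 visit applies to those leaving after Week 12. If that visit shows non-response, LOCF and non-responder imputation give the same result.
2. The same section waives withdrawal procedures for participants lost to follow-up or withdrawing consent. LOCF then reaches back to an earlier visit, which may have been a response.
3. A participant may attend the withdrawal visit and still meet a threshold such as EASI-50. That response is carried forward.
4. The protocol synopsis makes users of high-potency corticosteroids or systemic rescue non-responders from first use. Routes 2 and 3 therefore also require that no such rescue was used.

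**Size**

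Input: 13 participants enrolled in Cohort 1 (protocol section 4.1), all assumed dosed and so in the modified full analysis set. Changing k participants from response to non-response lowers the rate by k/13.

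- k = 1: 1/13 = 7.7 percentage points
- k = 2: 2/13 = 15.4 percentage points

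The shift applies at every scheduled visit after the participant leaves. The itch responder rate is restricted to participants with WI-NRS of at least 4 at baseline. If fewer than 13 qualify, one participant is worth more than 7.7 points.

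Illustration with an assumed rate, using the SAP's 95% Clopper-Pearson interval:

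| Responders | Rate | 95% interval |
|---|---|---|
| 6/13 | 46.2% | 19.2 to 74.9% |
| 5/13 (one changed) | 38.5% | 13.9 to 68.4% |
| 4/13 (two changed) | 30.8% | 9.1 to 61.4% |

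The shift is well inside the interval width. However, it runs in one direction, and section 6.8.2.2 prespecifies no sensitivity analysis for binary endpoints that would show it.

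**The case against.** The case for leaving the rule alone is substantial, and most of it stands.

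- **The trigger is usable.** A reader of sections 6.10.1.1 and 6.10.2 might infer that lack of efficacy can never be a reason for leaving the study, so that step 1 is empty. Section 7.1.5 contradicts that: it permits study termination on a section 6.10.1 ground and requires the ground to be recorded. Section 6.10.2 is also worded as description, and the eCRF reason codes are not in the documents.
- **It is not the sole protection.** The synopsis rescue rule is separate. The SAP also handles treatment discontinuation and rescue as intercurrent events before the missing-data steps. That text and Appendix 12.7 are redacted. They may already make a participant who stopped treatment for lack of efficacy a non-responder, so such a rule cannot be called absent.
- **LOCF often has a current status to carry**, because of the withdrawal visit.
- **Time since the last infusion does not measure exposure.** A reader might reason that dosing ends at Day 29, so no treatment-level reason can be recorded for the rest of the study. SAP section 6.6 records reasons for leaving the 12-week treatment period, and section 7.1.5 applies at any time.
- **The endpoints are exploratory and enrolment is closed.**

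These points narrow the problem without closing it. None of the readable text moves a participant in the third row of the table out of LOCF. The readable rescue rule does not reach someone who leaves without qualifying rescue.

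**Conclusion.** The point holds in a limited form. The visible rule for responder endpoints reads one of three recorded disposition reasons, so a participant with a documented efficacy failure at the other two levels can be handled by LOCF after leaving under a different reason. Each such participant who carries a response adds 7.7 percentage points at later visits, and two add 15.4.

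This rests on three assumptions: that all 13 enrolled participants are in the analysis set, that the redacted intercurrent-event text does not already cover the case, and that at least one such participant exists. The documents do not settle the last two. They do not support saying that responder rates are in fact inflated, or that step 1 can never apply. The primary safety endpoint and the secondary EASI endpoint are unaffected by this rule.

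**What to change.** 1. Restate step 1 of SAP section 6.8.2.2 so that non-responder imputation applies to all scheduled visits after study discontinuation when lack of efficacy is recorded as a reason at any disposition level: dosing period, treatment period or study. Observed visits of participants who stay in the study are not changed by this step.
2. Restate the exception in step 2 to match, so that no visit falls under both steps.
3. Reconcile protocol sections 6.10.2 and 7.1.5 with the SAP trigger, so that the place where lack of efficacy is recorded for a participant leaving the study is unambiguous.

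The change needs a few lines of text and uses reasons that section 6.6 already reports. If the redacted rule already has this effect, the change is redundant and harmless. The cost is that responder rates may be slightly lower.

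The change does not reach participants for whom lack of efficacy is recorded at no level. Recoding voluntary withdrawals from source notes is not recommended as a remedy: in an open-label study it would be a subjective judgement made with the outcome known.

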While the primary comparison of interest for efficacy endpoints will be within Cohort 2, for IMG-007 [REDACTED] versus placebo group, a broader comparison including 300 mg group versus placebo and the combined 300 mg and [REDACTED] versus placebo are also of additional, exploratory interest. For analysis within Cohort 1 (i.e., 300 mg group), efficacy comparison with baseline at each visit will be performed based on difference relative to zero. All analysis will use nominal two-sided significance level of 0.05.

For continuous efficacy endpoints, a mixed-effect model with repeated measures (MMRM) will be used. This model includes visit as a factor and respective baseline score as covariate for both Cohorts 1 & 2, and additionally treatment and treatment-by-visit interaction as factors for Cohort 2 only. Specific ways of handling data after receiving rescue medication or any other such clinical events will be performed.

For binary efficacy endpoints, if high potency corticosteroids or systemic rescue medications are used, the participant will be reported as a non-responder from the time such rescue medication is used.

Sensitivity analysis using other missing data handling approaches will also be performed. Further details including handling of specific intercurrent events and missing data imputations will be specified in the prospective statistical analysis plan (SAP).

PK Analyses

Serum concentration data will be tabulated and summarized (geometric mean, arithmetic mean, minimum, maximum, SD and % coefficient of variation) by treatment group for each visit at which samples were taken.

Immunogenicity Analyses

The immunogenicity results will be summarized using descriptive statistics by the number and percentage of participants who develop detectable ADA. The incidence of positive ADA will be reported for evaluable participants.

PD Analyses

Biomarker data will be listed by participant and visit/timepoint. Data for skin punch biopsy will be listed and summarized by visit.

Timing of Analyses

Timing of Analyses

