1. OVERVIEW

The purpose of the statistical analysis plan (SAP) is to ensure the credibility of the study results by pre-specifying statistical approaches for the analysis of this study. The SAP is intended to be a comprehensive and detailed description of strategy and statistical techniques to be used to realize the analysis of data for IMG-007-201. This SAP was written and finalized prior to the database lock, based on study protocol IMG-007-201 Version 6.0 (05Feb2024). Any methodological deviations from the protocol are documented. The analyses laid out in this SAP will be implemented by MeDaStats LLC for Inmagene Biopharmaceuticals.

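### LOCF carries responses into the off-drug follow-up for the key exploratory responder rates, and the SAP prespecifies no sensitivity analysis to test it

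*SAP*

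**What the plan says.** SAP 6.8.2.2 covers the binary key exploratory endpoints listed in SAP 4.5.2.1: EASI-50, EASI-75 and EASI-90, three IGA response definitions and the WI-NRS response, all by visit. It sets this order: "After the handling of intercurrent events explained above, missing data will be managed in two steps as given below". The intercurrent-event rules themselves are redacted. Step 1 imputes non-response after study discontinuation for lack of efficacy. Step 2 reads "LOCF approach will be applied for all missing visits, except for missing data that arises following study discontinuation with reason" lack of efficacy.

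On sensitivity analysis the section says: "No prespecified sensitivity analyses will be performed. Post-hoc sensitivity analysis will be considered as appropriate later".

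The current protocol (14 June 2024) says in the synopsis, directly after the rule for binary endpoints, and again in section 11.3.3: "Sensitivity analysis using other missing data handling approaches will also be performed". It leaves the details of missing-data handling to the SAP. For the secondary endpoint, SAP 6.8.1 does comply: "The following two sensitivity analyses will be performed". SAP section 5, on changes from the protocol, deals only with the loss of Cohort 2: "Analyses related to the placebo-controlled cohort (i.e., cohort 2) are no longer applicable and this will not be reported".

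**The concern.** Protocol 2.5.1 includes the 12-week follow-up so that the size and durability of response can be judged after dosing has stopped. For a participant who was responding when last seen and then leaves, LOCF does not measure durability; it assumes it. This applies to every reason for leaving except lack of efficacy, including death, unless the redacted intercurrent-event rules have already set the participant to non-response.

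The exception may be narrow. Protocol 6.10.2 lists consent withdrawal, non-compliance, an intercurrent or safety event, loss to follow-up and death as reasons for leaving the study. Lack of efficacy appears in Protocol 6.10.1.1 as a reason for stopping treatment. The eCRF reason codes are not visible, so this cannot be settled from the documents.

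An exit visit can refresh the carried value, but Protocol 6.10.2 waives it for consent withdrawal and loss to follow-up. Protocol 4.1 says Cohort 1 is meant to inform a Phase 2b design, so a durability figure from 13 people may carry weight. Without a prespecified check, the reader cannot tell how much of a Week 24 responder rate was observed and how much was carried forward.

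**Working it through.** The plan states no dropout rate, responder rate or power for these endpoints, so there is no plan figure to reproduce.

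**Inputs from the documents**
- 13 participants, Cohort 1 only (Protocol 4.1).
- Last dose on Day 29 (Protocol 6.4); follow-up visits on Days 113, 141 and 169 (Protocol 4.1).
- Mean terminal half-life of 31 days at 300-600 mg, from single doses in healthy participants (Protocol 2.2).
- Week 16 analysis window of Days 93-120 (SAP 12.6).
- 95% Clopper-Pearson intervals (SAP 6.8.2.2).

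**Timing**
- Weeks 16, 20 and 24 fall (113 - 29)/7 = 12, (141 - 29)/7 = 16 and (169 - 29)/7 = 20 weeks after the last dose.
- If exit visits are slotted by the SAP windows, one on Day 93 counts as Week 16 and is carried a further 169 - 93 = 76 days.
- Week 12 to Week 24 is 169 - 85 = 84 days, or 84/31 = 2.71 half-lives. With log-linear decline assumed, 0.5^2.71 = 15.3% of the Week 12 concentration remains.

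**Weight of one carried response**
- All 13 in the denominator: 1/13 = 7.7 points.
- The WI-NRS endpoint uses only participants with a baseline score of at least 4. For an assumed n of 12, 11 or 10 the step is 1/12 = 8.3, 1/11 = 9.1 or 1/10 = 10.0 points.
- For 1, 2, 3 or 4 carried responders (assumed range), LOCF exceeds non-responder imputation (NRI) by 7.7, 15.4, 23.1 or 30.8 points out of 13.

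**Illustration in both directions (assumed counts)**

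Suppose 6/13 respond at Week 12, three participants then leave, *j* of them are responders, and those who stay do not change. At Week 24:
- LOCF = 6/13
- NRI = (6 - j)/13
- observed cases = (6 - j)/10
- true rate between (6 - j)/13, if no leaver responds, and (9 - j)/13, if all leavers respond

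| j | LOCF % (95% CI) | NRI % (95% CI) | Observed % (95% CI) | Possible true % | LOCF error, points | NRI error, points | Observed error, points |
|---|---|---|---|---|---|---|---|
| 0 | 46.2 (19.2-74.9) | 46.2 (19.2-74.9) | 60.0 (26.2-87.8) | 46.2-69.2 | 0 to -23.1 | 0 to -23.1 | +13.8 to -9.2 |
| 1 | 46.2 (19.2-74.9) | 38.5 (13.9-68.4) | 50.0 (18.7-81.3) | 38.5-61.5 | +7.7 to -15.4 | 0 to -23.1 | +11.5 to -11.5 |
| 2 | 46.2 (19.2-74.9) | 30.8 (9.1-61.4) | 40.0 (12.2-73.8) | 30.8-53.8 | +15.4 to -7.7 | 0 to -23.1 | +9.2 to -13.8 |
| 3 | 46.2 (19.2-74.9) | 23.1 (5.0-53.8) | 30.0 (6.7-65.2) | 23.1-46.2 | +23.1 to 0 | 0 to -23.1 | +6.9 to -16.2 |

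LOCF gives the same 46.2% in all four rows, so it cannot show which row applies. The three results side by side can. No rule is unbiased throughout, so the case is for showing all three, not for swapping one for another.

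**The case against.** The case against is mainly about materiality.

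- **Safeguards exist.** The protocol synopsis makes users of high-potency corticosteroids or systemic rescue non-responders from that time, and the SAP does the same after exit for lack of efficacy. This stands and narrows the affected group. It does not cover someone who was responding, took no such rescue and left for another reason.
- **Other outputs help.** SAP 7.2 and 7.3 promise unimputed listings, SAP 6.6 gives reasons for discontinuation, SAP 6.8.3 reports PGIS, PGIC and DLQI response without imputation, and for the continuous endpoints "separate MMRM models will be developed to include all the post-baseline visits until Week 24/EOS". With 13 people, a reader of the full report could rebuild observed-case rates. But the listings leave that work to the reader, and the other analyses concern different endpoints.
- **The protocol mismatch is soft.** The protocol sentence does not name binary endpoints, it defers to the SAP, and the secondary endpoint does get two sensitivity analyses. The SAP (17 May 2024) rests on Protocol Version 6.0, whose wording is not visible. So the mismatch is with the current protocol only, and an omission from SAP section 5 against Version 6.0 cannot be shown. Still, Protocol 11.3.6 expects exploratory analyses to be generally similar to the primary and secondary ones, and here there are none of this kind.
- **Durability is plausible.** Protocol 2.5.1 cites class responses lasting up to 18 weeks after the last dose, which covers Weeks 16 and 20 but not Week 24. That is a reason to expect durability. It is not a reason to impute it unchecked.
- **Prespecifying now protects little in an open-label cohort.** This is partly true. However, if the last participant had Day 1 on 31 January 2024, Day 169 would be 17 July 2024, after the date of the SAP.

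It is also fair that every rate in the table lies inside the LOCF interval and that the counts are assumed.

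**Conclusion.** The concern holds and should be fixed. LOCF applies to the off-drug visits for every missing value not already set to non-response, and no prespecified analysis tests the resulting responder rates. Each carried responder moves the proportion by 7.7 points against NRI when all 13 count. With three leavers, the LOCF error can reach 23.1 points in either direction.

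This rests on assumed responder and dropout counts and on an unknown number of dropouts already handled by the redacted rules. The direction of the actual bias cannot be stated, and with no missing data all the rules agree. The endpoints are exploratory, single-arm and unpowered. The consequence is an unchecked description of durability; no confirmatory conclusion is at risk.

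**What to change.** Keep LOCF as the main rule if preferred. In SAP 6.8.2.2, replace the sentence that rules out prespecified sensitivity analyses with:

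> Two sensitivity analyses will be performed for each key exploratory responder endpoint, after the same intercurrent-event handling: (a) non-responder imputation at all scheduled visits after study discontinuation for any reason, including death, with LOCF only for intermittent missed visits; (b) observed cases. Both will be shown beside the LOCF result with the denominator, the 95% Clopper-Pearson interval and the number of imputed values per visit.

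The cost is one paragraph and a few tables, with no new data. NRI may give lower rates and is itself a conservative single imputation. Observed cases shrink the denominator and are fair only if dropout is unrelated to response. If the results have already been seen, the same two analyses should be reported and labelled post hoc.
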